### 13.3. EXPLORATORY ANALYSIS OF ADA ON PHARMACOKINETICS

The impact of ADA on PK will be explored graphically. Mean drug concentration-time plots for subjects with positive ADA at baseline and for subjects without positive ADA at baseline will be presented separately in both linear and semi-logarithmic scales.

Comparative descriptive statistics for the primary PK parameters will be presented as well.

## 14. Pharmacodynamics Analysis

Part A and combination of Part A and B will be analyzed.

Serum/plasma levels of PD variables at the time points pre-defined in the study protocol will be measured by validated methods and used for the PD analyses.

### 14.1. PHARMACODYNAMIC CONCENTRATION DATA

A listing of PD blood sample collection times and derived sampling time deviations will be provided.

Change from baseline PD variables will be calculated as (observed [measured] postdose value minus baseline value). Percent change from baseline will be calculated as (100 x change from baseline/baseline). Baseline is defined as the value observed on Day 1 (immediately before the start of the first infusion in Part A) or screening (for IgG, IgM, IgA).

Observed, change from baseline, and percent change from baseline in CD19+ B-cell counts, will be listed and summarized by study part, treatment, and scheduled visit using descriptive statistics (n, mean, SD, CV%, minimum, median, and maximum). Data from unscheduled visits will be listed but not summarized.

---

Document: \\ieedc-vnasc01\Biosdata\Archigen\SAIT101\YWA21301\Biostatistics\Documentation\SAP  
Author: Version Number: V2.0

Version Date: 13Feb2019

Template No: CS\_TP\_BS016 Revision 4  
Effective Date: 01Apr2016

Reference: CS\_WI\_BS005

Depletion of CD19+ B-cell counts (defined as a CD19+ B cell count below 20/ $\mu$ L) will be summarized with incidence by scheduled visit up to Week 52. Time to B-cell depletion (calculated as first time CD19+ B cell count below the limit of quantification (20 cells/ $\mu$ L) minus time of first dosing, rounded to nearest whole day) and duration of CD19+ B cell depletion (calculated as time of first return to non-depletion minus time of first depletion rounded to the nearest whole day) will be summarized for subjects in Part A. Time to B-Cell depletion will be summarized, and presented with Kaplan Meier curves and estimates of median depletion time with corresponding 95% CI. Duration thereof will be summarized only.

Observed and change from baseline in IgG, IgM, and IgA levels as well as CRP levels will be listed and summarized up to W24 CSR while for W52 CSR and onwards analysis, both initial first and second courses of study treatment groups will be considered using descriptive statistics described above.

Analyte CD19+ B cell count, IgG, IgM, IgA, and CRP data which fall below quantifiable concentrations will be set to zero for all summaries while missing values will be omitted.

Plots of serial mean and individual observed, change from baseline and percent change from baseline for CD19+ B-cell counts over time by treatment on linear scale will be provided: 1) up to Week 24; 2) from Week 24 to Week 52.

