**Treatment Regimen**

Each patient will receive first course which includes two intravenous (i.v.) 1,000 mg study drug infusions: one on Day 1 (Visit 2) and the second on Day 15 (Visit 5). Patients will receive an anti-pyretic and an anti-histamine, e.g., paracetamol and diphenhydramine or equivalent, 30 to 60 minutes before each infusion, plus 100 mg i.v. methylprednisone within 30 minutes prior to each infusion.

Patients with an inadequate response (<50% improvement from Baseline in both the swollen and tender joint counts) at Week 24 (Visit 12), will be eligible to receive the second course of two 1,000 mg i.v. infusions (one at Week 24 and the second infusion at Week 26 [14 days later]) of study drug.

On Day 1 and Day 15 (first and second infusions) blood PK samples and PD (CD19+ B-cell) samples will be collected before and 3 hours after the start of infusion and immediately (within 10 minutes) before and 1 hour after the end of infusion, at 48 hours after the start of each infusion (Days 3 and 17).

The PK/PD samples will also be taken at Weeks 4, 8, 12, 16, 20, and 24 to estimate elimination.

Blood PD samples will be additionally collected simultaneously at Weeks 36 and 52.

The main efficacy variable change from baseline in DAS28 (Disease Activity Score) will be evaluated on completion of 24 weeks of study assessments.

- All patients will be followed up for up to 52 weeks from the start date of the first infusion.
- Patients will attend the study center approximately every 12 weeks during Part B, from the start date of the second course of infusions. Patient who are not eligible for the second course of study treatment will also attend all visits until week 52.

Name of Sponsor/Company:	Archigen Biotech Ltd	
Name of Finished Product:	SAIT101 (proposed rituximab biosimilar)	
Name of Active Ingredient:	Rituximab	

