### **2.3.3 Pharmacodynamics**

- Depletion of CD19+ B cell count at Week 24
- Time needed to B cell depletion
- Duration of CD19+ B cell depletion
- % CD19+ B-cell count vs. baseline at Week 24
- AUC of CD19+ B-cell count change at Week 24
- Change from Baseline in CD19+ B cell count during the study period
- Change from Baseline in IgG, IgM, and IgA levels at Weeks 24 and 52
- Change from Baseline in CRP levels at Weeks 8, 16, 24, 36, and 52

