- n Questionnaires must be completed in the study center by the patient or patient's representative (in case patient is unable to read and/or write) based on the patient's verbal answers.
- o Joint assessor(s) will be independent to the rest of the study team.
- p To be performed by the central laboratory. Screening performed to confirm negative serology for HIV, HBV and HCV. Patients with negative HBsAg and positive HBcAb must have a HBV DNA level <20 IU/mL (or 112 copies/mL) by PCR test. These HBV patients must be willing to undergo PCR HBV DNA testing during treatment and may participate following consultation with a hepatitis expert regarding monitoring and use of HBV antiviral therapy, and provided they agree to receive treatment as indicated. An HBV re-test will be performed monthly including Day 1, Weeks 4, 8, 12, 16, 20, 24, 36,52, early EOS or unscheduled visit, if required. Patients who are confirmed positive and those who have active infections will be excluded from the participation in the study.
- q QuantiFERON Gold test is conducted at Screening. If TB is suspected at any time during the study, chest X-ray and/or QuantiFERON Gold test should be performed (Central Laboratory)
- r To determine presence of hypogammaglobulinemia (IgG <600mg/dL), which is an exclusion criterion.
- s On Day 1 and Day 15 (first and second infusions) blood PK and PD (CD19+ B-cell) samples will be collected before and 3 hours after the start of infusion and immediately (within 10 minutes) before and 1 hour after the end of infusion, **at 48 hours after the start of infusion (Days 3 and 17, in case of 2nd infusion at Day 16, the following PK sampling should be on Day 18)**. The PK and PD samples will also be taken (at the same time of the day first infusion started) at Day 8 (Week 1), Days 29 (Week 4), 57 (Week 8), 85 (Week 12), 113 (Week 16), 141 (Week 20), 169 (Week 24). PD sampling will be additionally collected at D 253 (Week 36), and 365 (Week 52, EOS). Window of each sampling is ± 10 minutes of the determined time points of Days 1, 3, 8, 15 and 17 and ± 3 hours at all other time points.

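### Rounding time to B-cell depletion to whole days hides any difference in onset within Day 1, which the protocol samples three times after the infusion starts

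*SAP*

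**What the plan says.** Protocol 2.3.3 lists "Time needed to B cell depletion" among the pharmacodynamic endpoints. SAP 14.1 takes the event as the "first time CD19+ B cell count below the limit of quantification" (20 cells/µL), calculates the interval "minus time of first dosing, rounded to nearest whole day", and has the result "presented with Kaplan Meier curves and estimates of median depletion time with corresponding 95% CI". No between-product test or margin is attached to it.

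On Day 1, footnote s of Protocol Table 2 asks for a pre-infusion CD19+ sample and then samples "3 hours after the start of infusion and immediately (within 10 minutes) before and 1 hour after the end of infusion". The next samples are at 48 hours and on Day 8. The Day 1 window is ±10 minutes, and Protocol 3.6.3.2 has the exact date and time of each sample entered in the eCRF. SAP 14.2 uses actual elapsed time, in hours, when it computes the area under the depletion curve (AUEC) from the same counts.

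**The concern.** The protocol places three post-start samples inside roughly the first five hours and times them to within minutes. The SAP then puts the result on a one-day grid before any summary is made. If depletion is mostly a Day 1 event, every arm would show a median of 0 days and a first Kaplan-Meier drop at time zero, whatever the order of onset within that day. In a similarity study, a reader could take matching zeros as evidence of matching onset when the derivation alone would have produced them.

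The change of depletion threshold from 14 to 20 cells/µL (SAP 2.6) can only bring the first crossing forward or leave it unchanged. It therefore moves the endpoint towards the range where the rounding matters, by an amount the documents do not give.

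**Working it through.** **1. Reproduce the infusion length.** From Protocol Table 1, eight 30-minute steps from 50 to 400 mg/h give (50 + 100 + … + 400) × 0.5 h = 900 mg in 240 min. The last 100 mg at 400 mg/h takes 15 min. The total is 255 min, as the table states.

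**2. Convert the scheduled samples to days and round.** Time zero is read as the start of the first infusion.

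| Sample | Hours | Days | Rounded |
|---|---|---|---|
| 3 h after start | 3.00 | 0.125 | 0 |
| Within 10 min before end | 4.08–4.25 | 0.170–0.177 | 0 |
| 1 h after end | 5.25 | 0.219 | 0 |
| 48 h | 48 | 2.0 | 2 |
| Day 8 | 168 | 7.0 | 7 |
| Day 15, pre-dose | 336 | 14.0 | 14 |

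**3. Does a longer or shorter infusion change this?** The last Day 1 sample falls at infusion length + 1 h and stays at 0 while that is under 12 h.
- Steps of 25 min: 237.5 min, last sample at 4.96 h, giving 0.
- Steps of 35 min: 272.5 min, last sample at 5.54 h, giving 0.
- Every rate halved: 450 mg in 240 min, then 550 mg at 200 mg/h = 165 min. The total is 405 min = 6.75 h, last sample at 7.75 h, giving 0.
- Break point: 12 − 1 = 11 h of infusion, a mean rate of 1,000/11 ≈ 91 mg/h.

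**4. What is lost and what is kept.** The documents do not give the share of patients depleted on Day 1, so five assumed patterns were simulated: 94 per arm (the randomized number), 400 runs, two-sided log-rank test at 0.05. The SAP plans no log-rank test. It serves here only to measure how much information the rounding removes.

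| Assumed pattern (arm 1 vs arm 2) | Power, rounded | Power, hours |
|---|---|---|
| A: 90% depleted on Day 1 in both; differ only within Day 1 | 0.04 | 0.99 |
| B: Day 1 share 80% vs 50% | 0.91 | 0.96 |
| C: Day 1 share 40% vs 20% | 0.87 | 0.89 |
| D: 100% on Day 1 in both; differ only within Day 1 | 0 | 1.00 |
| E: none on Day 1; 48 h share 60% vs 35% | 0.86 | 0.86 |

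In pattern A, 70%, 10% and 10% of one arm first deplete at the three Day 1 samples, against 20%, 20% and 50% of the other. The medians are 3 h and 5.25 h, a gap of 2.25 h, and both print as 0 days. In pattern D every rounded value is the same, so nothing is left to compare.

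**5. Do other outputs recover it?** Only in part. AUEC to Day 15 keeps actual times, but for patients already depleted by 5.25 h any difference in onset lies in the first 5.25 of 336 h, or 5.25/336 = 1.6% of the interval. Depletion incidence is tabulated by scheduled visit, and all three samples belong to Visit 2.

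**The case against.** A reader might infer that the endpoint cannot show any difference in onset between products. The documents do not support that. The rounded scale still separates Day 1, 48 hours, Day 8, Day 15 and later, and patterns B, C and E lose little or nothing. A reader might also blame the rounding if every arm reported a median of 2 days. That agreement would come from the sampling schedule: the first sample after Day 1 is at 48 hours, which is exactly 2 days, and unrounded times would agree just as closely.

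Three further points stand, at least in part. Nothing in the documents treats a difference of about two hours as relevant to similarity, and no decision rests on this endpoint: the primary objective is PK, and the pharmacodynamic measures given between-product confidence intervals are the AUECs. The underlying data are not destroyed, because collection times are listed and individual counts are listed and plotted. Finally, hour-level times carry some false precision. The recorded time is when a scheduled sample first reads low, and two of the three Day 1 samples are tied to the end of infusion, so they shift with infusion length. At 3 hours only 25 + 50 + 75 + 100 + 125 + 150 = 525 of 1,000 mg has been given on the Table 1 schedule. This is a reason to tabulate by nominal sample as well; it does not justify merging the three samples into one value.

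**Conclusion.** The point holds for differences within Day 1 and goes no further. The arithmetic is certain for any first infusion shorter than 11 hours. The practical size is not known: it runs from nothing, if no patient is depleted on Day 1, to complete loss of the ordering, if all are. A median of 0 days in every arm requires more than half of each arm to fall below 20 cells/µL by the last Day 1 sample, which is an assumption. The simulated powers rest on invented depletion patterns and show direction and range only. As the endpoint is secondary and descriptive, this is a cheap improvement and does not threaten the study's conclusions.

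**What to change.** In SAP 14.1:
- Calculate time to depletion in hours from the start of the first infusion, using actual sampling date and time, and drop the rounding for this variable.
- Report the median and the Kaplan-Meier curves in hours.
- Add a table by arm of the proportion depleted by each nominal Day 1 sample, by 48 hours and by Day 8. Because it uses nominal samples, it also deals with the dependence of the hour-level times on infusion length.

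The whole-day rule for duration of depletion can stay. The cost is one SAP sentence, a change of unit in one derivation and one short table. No new data are needed. The one small downside is that hour-level times partly reflect how long the infusion took, which a table footnote should say.

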## 14.2. PHARMACODYNAMIC PARAMETERS

For PD parameter calculations, predose samples that are BLQ for observed values will be assigned a numerical value of zero for calculation of change from baseline variables. For subjects with missing (i.e., non-evaluable samples) predose samples, change and percent change from baseline will not be calculated and PD parameters will not be reported. Any other observed BLQ values will be assigned as zero and any other observed missing values will be set to missing.

If calculable, the area under the depletion-time curve (AUEC) of CD19+ B cell count, will be calculated for change from baseline CD19+ B cell-time data by linear trapezoidal method using actual elapsed time from dosing. Negative partial areas will be calculated into the AUEC as observed, without exclusion or modification. All AUC parameters will be normalized to the time interval observed by dividing by the observed interval length.

AUEC(0-d15)                      AUEC (count·h) from time zero (predose immediately prior to 1st infusion) until Day 15 prior to infusion

AUEC(0-w24)                      AUEC (count·h) from time zero (predose immediately prior to 1st infusion) to Week 24

For both these parameters, the actual measurement time on Day 15 and Week 24 (predose), respectively, will be used for calculation (i.e., no adjustments will be made for any time deviations at this scheduled sampling time point). If the change from baseline value at those respective timepoints is missing, the respective parameters will be set to missing. The PD parameters will be summarized by treatment using n, mean, SD, CV%, minimum, median, maximum, and 95% CIs.

Pharmacodynamic parameters AUEC(0-d15) and AUEC(0-w24) will be compared between SAIT101 and both MabThera® and Rituxan® using analysis of covariance that includes a fixed effect for treatment and a covariate for baseline CD19+ B cell value. Least-squares mean for each treatment will be presented for each treatment with corresponding 95% CIs. The difference in least-squares means (SAIT101-MabThera® and SAIT101-Rituxan® and MabThera®-Rituxan) will be presented with corresponding 90% CIs.

The relationship of CD19+ B cell counts versus drug concentrations will be explored by scatter plot.

## 14.3. EXPLORATORY ANALYSIS OF ADA ON PHARMACODYNAMICS

The impact of ADA on PD (CD19+ B cells) will be explored graphically. Mean CD19+ B cell count-time plots for subjects with positive ADA at baseline and for subjects without positive ADA at baseline will be presented on linear scale.

---

Document:	\\ieedc-vnasc01\Biosdata\Archigen\SAIT101\YWA21301\Biostatistics\Documentation\SAP	
Author:		Version Number: V2.0
		Version Date: 13Feb2019
Template No:	CS_TP_BS016 Revision 4	Reference: CS_WI_BS005
Effective Date:	01Apr2016	

## 15. Efficacy Outcomes

All comparison for main and secondary efficacy variables between SAIT101 and MabThera® will be repeated for MabThera® and Rituxan® and SAIT101 and Rituxan® as exploratory analyses.

### 15.1. MAIN EFFICACY

#### 15.1.1. MAIN EFFICACY VARIABLE & DERIVATION

The main efficacy variable is the change from Baseline in DAS28-CRP at Week 24. The change from baseline in DAS28-CRP at Visit 24 will be calculated as follows:

Change at Visit 24= Value of DAS28-CRP at Visit 24 – Baseline value of DAS28-CRP

DAS28-CRP assessments consisted of tender joint counts (TJC), swollen joint counts (SJC) and C-reactive Protein (CRP). Formula is listed as follow or a calculator is available online at the following website: <http://www.das-score.nl/das28/DAScalculators/dascalculators.html>.

- $DAS28-CRP = [0.56 \times \sqrt{(TJC28)} + 0.28 \times \sqrt{(SJC28)} + 0.36 \times \ln(CRP+1)] \times 1.10 + 1.15$

TJC28: Tender Joint Count (28 joints); SJC28: Swollen Joint Count (28 joints); CRP(mg/L).

28 joints include proximal interphalangeal joints (10 joints), metacarpophalangeal joints (10 joints), wrists (2 joints), elbows (2 joints), shoulders (2 joints) and knees (2 joints).

DAS28-CRP will be considered missing if any of the three components is missing.

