### **2.3.2 Efficacy**

#### **Main Efficacy Endpoints**

- Change from Baseline in DAS28 at Week 24

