#### **Other Efficacy Endpoints**

- Change from Baseline in DAS28 at Weeks 8, 16, 36, and 52
- ACR20 response rates at Weeks 8, 16, 24, 36, and 52
- ACR50 response rates and ACR70 response rates at Weeks 8, 16, 24, 36, and 52
- Individual components of the ACR improvement criteria on Day 1 and at Weeks 8, 16, 24, 36, and 52
  - Swollen and tender joint count (the 66/68 joint count system)
  - Patient's assessment of pain (assessed on 1 to 100 mm Visual Analogue Scale [VAS])
  - Physician's global assessment of disease activity (assessed on 1 to 100 mm VAS)

- Patient's global assessment of disease activity (assessed on 1 to 100 mm VAS)
- Patient's assessment of disability (Health Assessment Questionnaire-Disability Index [HAQ-DI])
- CRP level
- Change from Baseline DAS28-CRP at Weeks 8, 16, 24, 36, and 52
- Major clinical response (continuous ACR70 for at least 24 weeks)
- Clinical remission (defined by SDAI < 3.3) at Weeks 8, 16, 24, 36, and 52
- Proportion of patients with European League Against Rheumatism (EULAR) response (good response, moderate response or no response) at Weeks 8, 16, 24, 36, and 52

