### **3.6.2.1.2 Patient's Global Assessment of Disease Activity**

Patients will mark on a VAS their overall assessment of how their RA has affected them, rating how they are managing from 0 (very well) to 100 (very poor). This is equivalent to the General Health component of the DAS (see Appendix 5).

Patients will sign and date the completed VAS.

Patient-reported outcomes and physician-reported outcomes should be completed independently of each other (to avoid bias of the Investigator or the patient).

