## 6 STATISTICS

### 6.1 Sample Size

The PK parameters reported from a recent study with rituximab in patients with RA revealed a percentage coefficient of variation (CV%) ranging from 26.3% for  $C_{\max}$  to 37.3% for  $AUC_{0-\infty}$ .

When the evaluable sample size in each group is 84, a three group design will have 81% power to reject both the null hypothesis that the ratio of test to standard geometrics means is below 0.800, and the null hypothesis that the ratio of test to standard geometrics means is above 1.250 (i.e., that the test and standard are not equivalent), in favor of the alternative hypothesis, that the means of the two groups are equivalent, assuming that the expected ratio of means is 1.000, that data will be analyzed in the log scale using analysis of variance (ANOVA) and that each one sided test is made at the 5% level. Each of the 15 hypotheses tests (five co-primary endpoints  $\times$  three pairwise comparisons (i.e., SAIT101 vs. MabThera®, SAIT101 vs. Rituxan®, MabThera® vs. Rituxan®)) are powered at 98% to 99.0% to yield 81% study-wide power.

Approximately 282 patients (94 patients per group) will be randomized in order to yield a minimum of 84 patients per group to account for a presumed 10% withdrawal.

This 94 patients in SAIT101 group and MabThera® group will provide 96% probability of declaring the equivalence in FAS with each one sided test at the 2.5% level, accounting for a presumed 1.0 standard deviation of DAS28 from the REFLEX study, and the equivalence margin of -0.6 to 0.6 chosen as the half of a clinical meaningful improvement of 1.2 in DAS28. Considering 18% withdraw from the REFLEX study, approximately 77 patients per group will provide approximately 91% probability of declaring the equivalence in the PP set with the same above assumption.

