**Appendix 5 DAS28 and EULAR Response Criteria**

**DAS28** is a formula combining:

- Tender Joint Count (28 joints)
- Swollen Joint Count (28 joints)
- ESR (mm/hour) or CRP (mg/L)
- General Health - Patient's Global Assessment of Disease Activity (VAS)

$$\text{DAS28-CRP} = [0.56 \times \sqrt{(\text{TJC28})} + 0.28 \times \sqrt{(\text{SJC28})} + 0.36 \times \log_{\text{nat}}(\text{CRP}+1)] \times 1.10 + 1.15$$

A calculator is available online at the following website:

<http://www.das-score.nl/das28/DAScalculators/dascalculators.html>

A representation and example is given below:

Based on the DAS28 score, disease activity is classified as:

≤ 2.6	Remission
>2.6 ≤ 3.2	Low disease activity
>3.2 ≤ 5.1	Moderate disease activity
>5.1	High disease activity

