#### 15.1.3. ANALYSIS OF MAIN EFFICACY VARIABLE

The primary objective of this study is to demonstrate equivalence in the SAIT101 and MabThera® in DAS28-CRP change from Baseline at Week 24. The equivalence between the two treatment groups will be declared if the two-sided 95% confidence interval (CI) of the difference in change from baseline in DAS28-CRP between SAIT101 and MabThera® is entirely contained within the equivalence margin of [-0.6, 0.6].

An analysis of co-variance (ANCOVA) model of change from baseline in DAS28-CRP at Week 24 with treatment group as factors and the baseline DAS28-CRP value as a covariate will be used to test the treatment difference of SAIT101 versus MabThera®. Least squares mean (LSM), standard error and two-sided 95% confidence interval for change from baseline will be reported for each treatment group. For the treatment difference, the LSM difference, standard error, and two-sided 95% confidence interval will be reported for both FAS and PP.

---

Document:	\\ieedc-vnasc01\Biosdata\Archigen\SAIT101\YWA21301\Biostatistics\Documentation\SAP	
Author:		Version Number: V2.0
		Version Date: 13Feb2019

Template No: CS\_TP\_BS016 Revision 4  
Effective Date: 01Apr2016

Reference: CS\_WI\_BS005

Value of DAS28-CRP and its change from baseline will also be listed.

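### Does applying the ±0.6 DAS28 margin to three-component DAS28-CRP loosen the efficacy equivalence test?

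*SAP*

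**What the plan says.** Protocol 2.3.2 gives the main efficacy endpoint as "Change from Baseline in DAS28 at Week 24". The other endpoints in that section include "Change from Baseline in DAS28 at Weeks 8, 16, 36, and 52" and, as a separate item, "Change from Baseline DAS28-CRP at Weeks 8, 16, 24, 36, and 52". Protocol 6.1 describes "the equivalence margin of -0.6 to 0.6 chosen as the half of a clinical meaningful improvement of 1.2 in DAS28" and assumes a standard deviation of 1.0. It ties neither figure to an ESR or a CRP version of the score.

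Protocol Appendix 5 describes DAS28 as combining two 28-joint counts, either ESR or CRP, and patient global. Section 3.6.2.1.2 says of the patient global scale: "This is equivalent to the General Health component of the DAS". The one formula printed in Appendix 5 is nevertheless three-component DAS28-CRP, without patient global.

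SAP 15.1.1 states "The main efficacy variable is the change from Baseline in DAS28-CRP at Week 24" and prints that same formula. SAP 15.1.3 judges the 95% interval for SAIT101 minus MabThera against ±0.6. DAS28-ESR, with patient global, is in 15.2.1 among the other efficacy variables. SAP 2.6 records only that a DAS28-ESR summary is added.

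**The concern.** If plain DAS28 in the protocol meant DAS28-CRP, four visits would be listed twice and Week 24 would be both main and other. Reading plain DAS28 as DAS28-ESR removes the duplication. The SAP would then have moved the equivalence test to a different score, kept the margin, and not listed the move in 2.6.

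The two scores are on different scales. The acute-phase term carries 0.36 × 1.10 = 0.396 per log unit in DAS28-CRP and 0.70 in DAS28-ESR. A 20 mm difference in patient global is 0.014 × 20 = 0.28 on DAS28-ESR and zero on DAS28-CRP. If differences shrink on the new score while the margin stays fixed, an arm at the limit of acceptability on the old score could pass too often.

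**Working it through.** **1. The plan's own power.** Inputs from protocol 6.1: margin 0.6, SD 1.0, one-sided 2.5% tests, 94 per group (FAS) and 77 per group (PP, 94 × 0.82). A true difference of 0 is assumed.

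Normal form: power = 2Φ(0.6 / (SD√(2/n)) − 1.96) − 1.
- n = 94: 0.6/0.1459 = 4.11, giving 96.9% (96.7% with the t distribution). Stated: 96%.
- n = 77: 0.6/0.1612 = 3.72, giving 92.2% (91.8% with t). Stated: about 91%.

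At a true difference of exactly 0.6 the t calculation gives 2.5%. The test holds its level for the declared score and margin.

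**2. The scale ratio under equal fractional change.** Formulas from SAP 15.1.1 and 15.2.1:
- DAS28-CRP = [0.56√TJC28 + 0.28√SJC28 + 0.36 ln(CRP+1)] × 1.10 + 1.15
- DAS28-ESR = 0.56√TJC28 + 0.28√SJC28 + 0.7 ln(ESR) + 0.014 GH

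Profiles (TJC28, SJC28, CRP mg/L, ESR, GH): floor 6, 6, 10, 28, 50; mid 15, 11, 25, 45, 65; high 22, 18, 50, 70, 80. The floor uses the entry minimums for joints, CRP and ESR, with the joints assumed to lie within the 28 and GH assumed. The other two profiles are wholly assumed.

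Mid profile, everything halved:
- Joints: (2.169 − 1.534) + (0.929 − 0.657) = 0.907.
- DAS28-CRP change: 1.10 × (0.907 + 0.36 × 0.655) = 1.258.
- DAS28-ESR change: 0.907 + 0.7 × 0.693 + 0.014 × 32.5 = 1.847.
- Ratio: 1.258/1.847 = 0.681.

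| Profile | 20% | 50% | 70% |
|---|---|---|---|
| Floor | 0.620 | 0.628 | 0.629 |
| Mid | 0.668 | 0.681 | 0.689 |
| High | 0.676 | 0.692 | 0.703 |

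On a wider assumed grid (TJC28 6-28, SJC28 4-24, ESR 28-80, CRP 5-60, GH 30-90; falls of 10-70%) the ratio runs from 0.48 to 0.85. About 42% of grid points fall within 0.62-0.70.

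**3. What that would imply.** Take a DAS28-ESR improvement of 1.9 in one arm and 1.3 in the other. The 1.9 is the rituximab figure in protocol 1.3.2, where the score is called only DAS, so ESR is an assumption. The DAS28-CRP difference is then 0.381, 0.417 or 0.422. The chance of passing ±0.6 is:
- SD 1.0: 23-32% at n = 94 and 19-27% at n = 77.
- SD shrinking with the score: 41-65% and 34-57%.

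Both sets must pass under protocol 6.4, so the PP figure is the ceiling.

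**4. The ratio under unequal change.** Mid profile, joints −50%, CRP −70%, ESR −30%, GH −20%:
- DAS28-CRP change: 1.10 × (0.907 + 0.36 × 1.118) = 1.441.
- DAS28-ESR change: 0.907 + 0.7 × 0.357 + 0.014 × 13 = 1.339.
- Ratio: 1.076.

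Across the three profiles this pattern gives 1.06-1.08, and a change in joints alone gives 1.10. A change in patient global alone gives 0. Direction as well as size depends on which components move.

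**5. Which score does the margin belong to?** Evidence for DAS28-ESR: the duplicated listing, and patient global named as a component. Evidence for DAS28-CRP:
- The protocol's endpoint lists never mention DAS28-ESR.
- Appendix 5 prints only the three-term DAS28-CRP formula, followed by a EULAR table with cut-offs of 1.2 and 0.6. SAP 15.2.1 applies that table to DAS28-CRP.
- SAP 2.6 calls DAS28-ESR an addition, so its authors did not read it as already in the protocol.
- Double listing is not unusual here: CRP at Weeks 8, 16, 24, 36 and 52 appears both as an ACR component (2.3.2) and as a pharmacodynamic endpoint (2.3.3).

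The sources of the 1.2 and the SD of 1.0 are cited publications that cannot be consulted here. The illustration announced in Appendix 5 is also missing from the text available.

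**The case for a change.** The strongest reply is that the visit patterns match too well for chance. In the SAP, DAS28-CRP takes exactly the visits the protocol gave to plain DAS28, and DAS28-ESR takes exactly the visits the protocol gave to DAS28-CRP. That looks like an exchange of scores. Even if plain DAS28 always meant DAS28-CRP, nothing shows that the 1.2 or the SD of 1.0 came from a score without patient global. Under equal fractional change every ratio computed is below 1, so any error would usually favour a finding of equivalence.

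Some of this stands. The protocol should have named its variant, and SAP 2.6 is silent on the choice. The scales do differ, and the leniency would be material if the margin had been set on DAS28-ESR and components moved together.

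The step from there to a fault in the plan does not stand. It needs the ESR premise, which is an inference against the only printed formula. It also needs a pattern of change that is assumed. Neither available remedy is clearly better. Making DAS28-ESR the main variable would act on that inference and replace a centrally measured CRP with an ESR measured locally (protocol 3.6.2.2). A margin rescaled to 0.42 rests on assumed profiles rather than a clinical argument, and at SD 1.0 it leaves 63% power in FAS and 47% in PP.

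**Conclusion.** No change to the plan follows. The protocol left the DAS28 variant open, and the SAP filled the gap with the score whose formula the protocol prints, fully specified. For that score and ±0.6 the level is 2.5% per side, and the stated power reproduces to within a point.

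The 19-32% pass rates describe a different score. They hold only if the margin was set on DAS28-ESR, all components change by the same fraction, the baselines are as assumed and the SD is 1.0. The documents establish neither of the first two conditions, and plausible departures take the ratio from 0.48 to above 1.

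A reader who prefers the four-component score is already served. SAP 15.2.3 gives DAS28-ESR the same ANCOVA with its own baseline in FAS and PP, including Week 24, and that interval can be read beside ±0.6. A line in SAP 2.6 naming the variant would tidy the record but would alter no analysis. The conclusion would differ if the cited sources showed that 1.2 and 1.0 were DAS28-ESR figures, which cannot be determined from the protocol and SAP.
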